1.2 Study Population and Eligibility Criteria

The sources of cases for this study were inpatients and outpatients admitted from 1 July 2022 to 30 June 2025 with negative expression of driver genes in postoperative stage IIA-IIIA lung adenocarcinomas with qi and yin deficiency. Inclusion for observation should be no later than 6 weeks postoperatively. Screening will be based on inclusion and exclusion criteria (Table 1).

Table 1. Study Inclusion and Exclusion Criteria.

Inclusion criteria	Exclusion criteria

① Patients with clinical staging of stage IIA-IIIA lung adenocarcinoma after radical surgery, patients within 6 weeks after surgery;
 
② Driver gene negative (no EGFR, ALK, ROS1 mutations), PD-1/L1 expression <1%;
 
③ Fulfilling the diagnostic criteria for the lung qi and yin deficiency type, the primary symptoms are cough, low sputum, shortness of breath, low or muffled voice, weakness, and thirst without wanting to drink. Secondary symptoms include spontaneous sweating, nocturnal sweating, five heartburns, red tongue or teeth marks on the sides of the tongue, and a weak pulse. At least two primary symptoms and one of the secondary symptoms are present;
 
④ Patients aged between 18 and 75 years;
 
⑤ Patients with basically normal blood and biochemical indicators, without serious viral or bacterial infections; without organ failure and serious
	
① Patients with incomplete resection or whose cancer has undergone recurrence or metastasis;
 
② Patients who are being treated with other drugs or therapies (including other Chinese herbal medicines, immunological drugs, radiotherapy, etc.);
 
③ Patients who are themselves mentally ill and have a lack of autonomous behaviour;
 
④ Women who are pregnant, preparing for pregnancy or breastfeeding;
 
⑤ Combined heart, lung, brain, liver, kidney and haematopoietic system and other serious diseases, psychiatric patients;
 
⑥ Allergic or known hypersensitivity to the components of the drug;
 
⑦ Patients who are participating in other clinical trials or have participated in other clinical trials within 3 months;
 
⑧ Alcohol and/or psychoactive substances abuse, drug

heart disease (TBIL <68 μ mol/L, AST <90 IU/L, CREA <350 μ mol/L, WBC >3.5 \times 10 ⁹ /L and < 12 \times 10 ⁹ /L, PLT >80 \times 10 ⁹ /L, HCT >0.20)	abusers and dependent persons;

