OS: Endpoint indicator, defined as the time from the start of randomisation to death due to any cause. Overall survival and median survival calculations were performed with observational follow-up up to 5 years postoperatively. MRD: Second-generation sequencing NGS method is used to detect MRD in peripheral blood of the study subjects to obtain the superior population screening model for TCM treatment; Circulating tumour cell detection: Detect 1 time each before and after intervention. Specimen collection method: 10ml of venous blood was taken from the patient's median elbow vein with EDTA blood collection tube, the blood collection tube was repeatedly inverted and mixed, centrifuged at 2000g for 10min, the supernatant was retained, and in order to further remove the redundant cellular components, it should be centrifuged again at 8000g for 10min. Separated plasma was frozen and stored at -80°C or extracted immediately according to the extraction kit instruction steps respectively. The remaining blood cells should be added to saline to replenish 10ml and then immediately isolate the circulating tumour cells. TCM symptom score: According to the "Shanghai TCM disease diagnosis and treatment routine", 10 TCM symptoms of cough, sputum, chest pain, chest tightness, shortness of breath, fatigue, loss of appetite, insomnia, dry mouth and throat and spontaneous sweating were observed, and the severity was scored according to 0-3, which was recorded once before and 6 months after the intervention. Significant effect: the reduction of TCM symptom score is greater than or equal to 70% after the intervention; Effective: the reduction of TCM symptom score is greater than or equal to 30% and less than 70% after the intervention; Ineffective: the reduction of TCM symptom score is less than 30% after the intervention or elevated compared with the previous one. Quality of life assessment: The Quality of Survival Scale for Lung Cancer Patients EORTC QLQ-LC43 was used, which consists of EORTC QLQ-C30 (core scale) and EORTC QLQ-LC13 Th (characteristic subscale of lung cancer). It mainly scores lung cancer patients on 5 domains related to functioning, general clinical symptoms, characteristic sub-symptoms, general health status and

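### The TCM symptom score is judged by percent reduction from a baseline with no minimum, so at low baselines one point decides the grade; a baseline-adjusted comparison of the score would avoid this

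*Protocol*

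**What the plan says.** Section 2.6.4 lists the TCM symptom score among the secondary efficacy indicators. Its items are "10 TCM symptoms of cough, sputum, chest pain, chest tightness, shortness of breath, fatigue, loss of appetite, insomnia, dry mouth and throat and spontaneous sweating". On rating and timing, the same section says "the severity was scored according to 0-3, which was recorded once before and 6 months after the intervention". Three grades follow. The top one, Significant, needs a fall of 70% or more from the starting score. The middle one is worded as "Effective: the reduction of TCM symptom score is greater than or equal to 30% and less than 70% after the intervention". The bottom one takes in every smaller fall and also any rise, in these words: "Ineffective: the reduction of TCM symptom score is less than 30% after the intervention or elevated compared with the previous one".

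Entry is set in section 1.2, inclusion criterion 3. There "the primary symptoms are cough, low sputum, shortness of breath, low or muffled voice, weakness, and thirst without wanting to drink". For the second tier, the criterion says "Secondary symptoms include spontaneous sweating, nocturnal sweating, five heartburns, red tongue or teeth marks on the sides of the tongue, and a weak pulse". The number needed to qualify is put as "At least two primary symptoms and one of the secondary symptoms are present". It carries no severity threshold and no minimum score.

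The Statistical Analysis section gives generic methods by data type. Measurement data get a two-sample t-test, or a rank-sum test if not normal, with paired tests within group. Grade data get the Wilcoxon rank-sum test. It does not say which type this endpoint is, and no adjustment for baseline is mentioned.

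**The concern.** A percent reduction has the baseline score as its denominator, and nothing in the entry criteria keeps that denominator away from very small values. Several entry symptoms are not scored at all, and several scored symptoms play no part in entry. The grade a patient receives can therefore depend as much on how low the patient started as on how much the symptoms changed.

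At stake is the readability of the one secondary endpoint that measures TCM symptoms, and some precision in comparing the groups on it.

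**Working it through.** **Inputs.** Items, 0-3 rating and grade cut-offs come from section 2.6.4; entry symptoms from section 1.2. Assumption: the total is the unweighted sum, so 0 to 10 × 3 = 30, since the protocol states neither a total nor weights. The plan gives no figure to reproduce on this point.

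**Step 1: the two lists side by side.**

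| Entry symptom | Score item |
|---|---|
| Cough | Cough |
| Low sputum | Sputum, approximately; scanty sputum might rate 0 |
| Shortness of breath | Shortness of breath |
| Low voice | None |
| Weakness | Fatigue, approximately |
| Thirst | Dry mouth and throat, approximately |
| Spontaneous sweating (secondary) | Spontaneous sweating |
| The other four secondary symptoms or signs | None |

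Chest pain, chest tightness, loss of appetite and insomnia are scored but are not entry symptoms.

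**Step 2: lowest baseline compatible with entry.** A minimal profile is two of six primary symptoms and one of five secondary ones: C(6,2) × 5 = 15 × 5 = 75 profiles. Suppose no other scored symptom is present. If u primary symptoms go unscored, the profiles with no scored symptom number C(u,2) × 4, because four secondary symptoms are unscored.

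| Matching of the lists | u | Profiles at zero |
|---|---|---|
| Broad: only low voice unscored | 1 | 0 of 75 |
| Low sputum also rates 0 | 2 | 4 of 75 |
| Thirst (or weakness) also not matched | 2 | 4 of 75 |
| Low sputum rates 0 and thirst not matched | 3 | 12 of 75 |
| Exact names only | 4 | 24 of 75 |

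Under the broad matching, the 75 profiles contain one scored symptom in 20, two in 45 and three in 10. With each rated 1, the baseline is 1, 2 or 3 points. Baselines of 1 to 3 are thus possible even under the most generous matching. These are counts of profiles, not of patients.

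**Step 3: what the grades require.** For an integer baseline B above 0, a drop of at least ceil(0.3 × B) points reaches 30%, and at least ceil(0.7 × B) reaches 70%.

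| Baseline | Smallest drop for Effective | Smallest drop for Significant | Grade of a one-point drop |
|---|---|---|---|
| 1 | not reachable | 1 | Significant (100%) |
| 2 | 1 | 2 | Effective (50%) |
| 3 | 1 | 3 | Effective (33%) |
| 4 | 2 | 3 | Ineffective (25%) |
| 10 | 3 | 7 | Ineffective (10%) |
| 30 | 9 | 21 | Ineffective (3%) |

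At baseline 1 both thresholds equal one point, so the middle grade is empty.

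**Step 4: baseline zero, if it occurs.** A rise is Ineffective, because that grade includes an elevated score. A score that stays at zero gives 0/0 and has no grade. No patient at zero can improve.

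**Step 5: direction of the power difference.** Illustrative simulations used 160 per arm and ten correlated 0-3 items, with effect, correlation and baseline level all assumed. ANCOVA on the 6-month score had more power than the rank-sum test on the three grades in every scenario, but the gap ran from about 3 to 26 percentage points. With an assumed baseline-to-follow-up correlation of 0.6 and mean baselines of about 3 to 9, the grades reached 81%, 92% and 95%, against 82%, 90% and 91% for an unadjusted t-test on the 6-month score. In that setting the shortfall against ANCOVA comes from the missing baseline adjustment, not from the grading. With a correlation of 0.3, or very low baselines, grading itself cost power.

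**The case against.** The endpoint is named as the score, the score is recorded at both times, and the Statistical Analysis section offers tests for measurement data. A reader might infer that the plan throws the score away in favour of three classes. The documents do not show that, because nothing limits the endpoint to the grades. The objection stands on this. What remains is that the grades are the only outcome rule stated for this endpoint, and the tests available for the raw score ignore baseline.

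A reader might also infer that the entry criteria plainly admit zero baselines and so leave the grade undefined. That too goes beyond the text. Five of the six primary symptoms have a natural counterpart in the score, and two primary symptoms are required, so under the broad matching at least one is always scored. Zero needs a narrower matching and no other scored symptom, in patients within six weeks of lung surgery. Item anchors may also be fixed in the diagnostic routine that section 2.6.4 cites, which is not at hand.

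Finally, percent-reduction grades are customary, this is one of about ten secondary indicators, and the choice of covariates is commonly left to the SAP, which is not shown. That limits the weight of the point. It does not remove it, because the grade and its cut-offs are fixed in the protocol itself.

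**Conclusion.** The point holds for low baselines: they are compatible with entry under the broad and the narrower matchings alike, and the grade then turns on a single point. This rests only on the protocol's cut-offs and on an unweighted sum.

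The zero-baseline problem is conditional on how the two lists correspond, which the protocol does not state, and even then only a score that stays at zero is ungraded. How many patients would start at 0 to 3 points cannot be computed.

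That baseline adjustment gains power over the grades is supported in direction. A reader might want to attach a figure for the loss to this trial. The documents give no baseline distribution, correlation or expected effect for the score, so no such figure should be quoted.

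DFS, the sample size and the primary conclusion are untouched. This is a worthwhile, inexpensive improvement to a secondary endpoint.

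**What to change.** In section 2.6.4 and the Statistical Analysis section, name the between-group comparison for this endpoint: the 6-month total score (0-30), compared by ANCOVA with the baseline score as covariate and including any patients at baseline 0. Report the 70%/30% grades descriptively among patients with baseline above 0, and show the number at baseline 0 by arm. One sentence stating that the total is the sum of the ten items, and how the entry symptoms correspond to them, would settle whether zero can occur.

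The cost is wording only, since the same CRF data serve. The downside is that the customary effective-rate grading becomes descriptive.

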
2.7 Safety Assessments

2.7.1 Safety background information related to the medicines used in the trial

According to the preclinical study, clinical trial information and drug composition, it is necessary to pay attention to the observation of the changes in the haematopoietic system, digestive system and urinary system of the patients during the trial, such as the number of red blood cells, haemoglobin content, blood creatinine and urea nitrogen, liver function and so on.

2.7.2 Observation and recording of adverse events

Observation and recording: The investigator should carefully observe any adverse events occurring in the subjects during the clinical study period, and require the subjects to truthfully reflect the changes in their condition after the administration of the drug, avoiding induced questions. While observing the efficacy, pay attention to the observation of adverse events or unanticipated toxic side effects (including symptoms, signs and laboratory tests). Regardless of whether the adverse event is related to the test drug or not should be recorded in detail in the CRF form, including the time of the appearance of the adverse event, symptoms, signs, degree, duration,

laboratory test indexes, treatment methods, after, results, follow-up time, etc., and should be recorded in detail in the case of the combined use of medication, in order to analyse the relevance of the adverse event to the test drug, the record should be signed and dated. Medical treatment of subjects: When adverse events are detected, the investigator may take necessary treatment measures according to the condition, such as adjusting the dosage, temporarily interrupting the medication, etc., and decide whether to terminate the trial. In the event of serious adverse events, the unit undertaking the trial study must immediately take the necessary treatment measures to protect the safety of the subjects.

2.7.3 Judgement of severity

Mild: mild discomfort, the subject can tolerate does not affect the treatment, do not need special treatment, no effect on the subject's recovery. Medium: moderate discomfort, intolerable to the subject, requiring special treatment, and having a direct impact on the subject's recovery. Severe: severe discomfort, endangering the life of the subject, death or disability, requiring immediate emergency treatment.

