2.7.9 Reporting and Handling of Adverse Events

The occurrence of any adverse event, such as the subjective discomfort of patients and abnormal laboratory tests, should be taken seriously, carefully analysed, and immediate measures should be taken to protect the safety of the subjects. Record in detail in the CRF form and retest in 24 hours

and 7 days and 14 days as appropriate. Record its persistence, regression and disappearance. Handling of Serious Adverse Events: Any serious adverse event that occurs during the trial must be reported immediately to the Medical Ethics Committee of the lead unit or the principal investigator by completing the Serious Adverse Event Report Form (SARF), and in the case of serious adverse reactions, to the State Food and Drug Administration (SFDA) within 24 hours. Notify the telephone number and contact person of the unit listed in the CRF form. When a patient has an emergency, the principal investigator of the research unit can open the emergency letter of the corresponding number taken by the patient (but there must be two witnesses present, and make corresponding records), according to the drug and the symptoms of the appropriate treatment, and notify the clinical monitor of the results of the treatment, and the researcher should be recorded in the case report form in detail on the reason for the breakthrough of blinding, date, treatment, results and sign. All adverse events should be followed up until they are properly resolved or the condition is stabilised. The method of follow-up can be inpatient, outpatient, home visit, telephone, or newsletter, depending on the type and severity of the adverse event.

Statistical Analysis

Statistical software such as SPSS 25.0 and GraphPad Prism were used for data analysis and statistical graphing in this study, with a test level of α taken as 0.05 and two sided test, giving point estimates and 95% confidence intervals.

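### The adverse-event severity scale in 2.7.3 rests on discomfort and has no laboratory criteria, so symptom-free laboratory toxicity that needs treatment without endangering life fits no level

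*Protocol*

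**What the plan says.** Section 2.7.3 of the protocol sets three levels of adverse-event severity:

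- "Mild: mild discomfort, the subject can tolerate does not affect the treatment, do not need special treatment", with no effect on recovery.
- "Medium: moderate discomfort, intolerable to the subject, requiring special treatment, and having a direct impact on" recovery.
- "Severe: severe discomfort, endangering the life of the subject, death or disability, requiring immediate emergency treatment".

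Section 2.7.1 names the risks to watch: "it is necessary to pay attention to the observation of the changes in the haematopoietic system, digestive system and urinary system". Its illustrations are "such as the number of red blood cells, haemoglobin content, blood creatinine and urea nitrogen, liver function and so on".

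Section 2.7.2 tells the investigator to look for "adverse events or unanticipated toxic side effects (including symptoms, signs and laboratory tests", and lists degree among the items to record on the CRF for each event. Section 2.7.9 gives as examples of adverse events "such as the subjective discomfort of patients and abnormal laboratory tests, should be taken seriously", so laboratory abnormality stands beside discomfort as a separate kind of event. Section 2.6.3 schedules blood, liver and kidney tests monthly on treatment and every 6 months in follow-up.

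Section 2.7.9 also says that a serious adverse event "must be reported immediately to the Medical Ethics Committee of the lead unit or the principal investigator".

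**The concern.** The protocol asks for a severity grade on a kind of event that its scale was not written to grade. A rise in creatinine or a fall in haemoglobin often has to be judged from the number, because the patient may feel nothing. The scale offers no number. It asks first how much discomfort there is and whether the patient can bear it.

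This bears on the risks the protocol itself singles out, in patients who are all to receive platinum-based chemotherapy (2.2). If the scale gives no answer, each investigator at the five centres listed in 1.4 has to improvise one. The grade is also used in the conduct of the trial: 2.7.9 lets the manner of following up an event depend on its type and severity.

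**Working it through.** No arithmetic applies, since the protocol states no figure that depends on the scale. The check is to set the sections side by side and then try events against the three levels.

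**Counts.** Examples of risk in 2.7.1: red cells, haemoglobin, creatinine, urea nitrogen, liver function. That is 5 of 5 laboratory measures. Levels in 2.7.3 with a laboratory criterion: 0 of 3. No other severity scale or laboratory grading threshold appears anywhere in the protocol. The laboratory limits in 1.2 are eligibility limits.

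**What each level requires.** Mild: tolerable, treatment unaffected, no special treatment, no effect on recovery. Medium: moderate discomfort that the patient cannot tolerate, special treatment, *and* an effect on recovery. Severe: severe discomfort, danger to life, death or disability, emergency treatment. The Severe items are most naturally alternatives, because death and disability cannot sensibly be required together with discomfort.

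**Trial events, all symptom-free laboratory abnormalities:**

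| Event | Mild? | Medium? | Severe? | Result |
|---|---|---|---|---|
| (a) Needs treatment, life not in danger | No: special treatment is needed | No: not intolerable, no moderate discomfort | No: no danger to life, no disability, no emergency | No level fits |
| (b) Large, untreated, not yet dangerous | Yes, by default | No | No | Mild, the same as a trivial change |
| (c) Endangers life | No | No | Yes, through danger to life | Severe |
| (d) Small, untreated | Yes | No | No | Mild, which is reasonable |

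The scale works for (c) and (d). It fails for (a), where the text excludes every level, and for (b), where nothing in the text separates a large abnormality from a small one. These two make up the middle of the range.

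**The case against.** Several points on the other side are sound and set the limits of this one.

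*A reader might infer that severity is graded only by what the patient feels.* The text does not support that. Need for treatment, effect on treatment and recovery, danger to life, death, disability and need for emergency care all appear in 2.7.3. Nor does it follow that a life-threatening silent toxicity is graded Mild or cannot be graded: case (c) shows that it can be Severe.

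*An investigator could read the Medium items as alternatives*, so that need for treatment alone would place case (a) there. That is possible in practice, but the sentence joins the items with *and*. If some investigators read it one way and some the other, that is the inconsistency at issue. It would also leave case (b) where it is.

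*A reader might infer that a between-arm difference in blood, liver or kidney toxicity would be missed.* That goes too far. The protocol specifies no severity tables. The adverse-event incidence it fixes in 2.7.4 depends on causality, not severity. Laboratory values are collected on schedule (2.6.3) and laboratory indices are recorded for each event (2.7.2), so the measurements can still be compared. What suffers is the grade.

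*A reader might measure the problem by the number of scheduled panels*: 356 patients × 6 monthly tests = 2,136. That counts planned tests if every patient completes six months, not events wrongly graded.

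*On serious events*, no section says that serious means Severe. Section 2.7.9 uses serious as its own term with its own report form, and the trial is placed under GCP. Section numbering runs from 2.7.4 to 2.7.9, so a definition may have stood in a part that does not appear. It would therefore be wrong to say that a hospital admission is Medium and goes unreported. What stands is narrower: the text at hand does not define serious, and the only nearby wording about death, disability and danger to life sits inside the Severe level, which invites confusion of the two.

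**Conclusion.** The point holds in a limited form. The scale in 2.7.3 is anchored on discomfort and tolerability and has no laboratory criteria, although the protocol's own examples of risk are all laboratory measures and it requires abnormal laboratory tests to be recorded with a degree. Symptom-free toxicity in the middle range either fits no level or falls to Mild by default, so severity data for the named risks would be inconsistent between investigators and centres.

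The size is 0 of 3 levels with a laboratory criterion against 5 of 5 laboratory examples. The number of events affected cannot be estimated, because the protocol gives no rate of laboratory abnormality. The conclusion assumes that the Medium items apply jointly, as written, and that the Severe items are alternatives. Raw values, incidence under 2.7.4 and the grading of life-threatening events are not affected.

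This should be corrected, but it does not touch the primary analysis. It belongs in the protocol rather than an analysis plan, because investigators assign the grade when they record the event. The lack of a definition of serious, and the choice of recipient in the reporting rule, are secondary.

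**What to change.** In 2.7.3, grade laboratory adverse events from the recorded value on a standard numeric toxicity scale, for example CTCAE with the version named. For symptoms, either keep the present three levels or use the same scale. The choice of scale rests with the investigators.

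Secondary, in 2.7.9:

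- State that a serious adverse event is defined by outcome (for example death, danger to life, hospital admission, disability) and is a separate matter from the Severe level in 2.7.3.
- Change the reporting rule from the Ethics Committee *or* the principal investigator to the Ethics Committee *and* the principal investigator. As written, the committee need not be told.

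The cost is a wording change to the protocol and the CRF. The laboratory values are already collected, so grades can be derived by program, including for patients already enrolled. The downside is that more events will be graded above Mild, and a stated definition of serious may bring more reports.
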